## STATISTICAL ANALYSIS

Statistical analysis will be performed by the DDSI statistician listed in this protocol, who will determine the appropriate statistical tests for each outcome of interest. Categorical variables will be reported using proportions and analyzed using Pearson's Chi-square. Continuous variables will be reported using median and interquartile range due to their non-parametric nature and examined using either a Student's t-test or a Wilcoxon signed rank test. Pain scores,

opioid requirements, hospital length of stay, and PRQOL requirements will be compared using Mann-Whitney U tests.

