## OUTCOMES OF INTEREST

### **Primary outcomes of Interest**

Primary outcomes of interest are opioid requirements and pain scores over initial 72 hours of the postoperative period. Opioid requirements will be assessed by measuring the cumulative dose of opioids administered intravenously (infused through a patient-controlled analgesia device as well as the quantity of opioids administered intravenously as rescue, if needed) and the quantity of opioids administered through oral preparations. This will be assessed at time points: at day of surgery (while patients are at PACU or the nursing floor), at postoperative days 1, 2 and 3. Additional time points include daily assessments during the rest of the hospital stay up to a maximum of 7 days. The total dose of opioids used at each time point will be recorded and converted into morphine equivalents for standardization and analysis. We will record the cumulative dose of opioids from 0 hours to 72 hours after the operation and for the total hospital length of stay (up to a maximum of 7 days). In addition, we aim to record the dose of opioids administered intra-operatively by the anesthesiologist, time for first oral opioid dose over the first 72 hours (discontinuation of PCA), and the percentage of patients not requiring opioids over the first 72 hours.

Pain scores will be determined using a 100mm visual analog scale (VAS). The VAS is a 100mm horizontal line with two endpoints: 0 (no pain) and 100 (worst imaginable pain). While in the hospital, subjects are to assess, “How much pain are you experiencing right now?” Pain scores will be assessed at baseline during preoperative evaluation, at day of surgery (PACU or nursing floor), at postoperative days 1, 2 and 3. Additional time points include daily assessments during the rest of the hospital stay up to a maximum of 7 days.

Additional pain scores will be obtained using the Patient-Reported Outcome Measurement Information System (PROMIS) Pain Intensity 3a survey, which is part of the

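### The plan does not say how four VAS readings form one 72-hour pain result, leaves the collected baselines for pain and quality of life unused, and names a paired test for independent arms

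*Combined protocol and SAP*

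**What the plan says.** **Pain as an outcome.** The Primary outcomes of Interest section states: "Primary outcomes of interest are opioid requirements and pain scores over initial 72 hours of the postoperative period". On timing it says: "Pain scores will be assessed at baseline during preoperative evaluation, at day of surgery (PACU or nursing floor), at postoperative days 1, 2 and 3". Further readings follow daily up to 7 days. The in-hospital question is tied to the stay ("While in the hospital, subjects are to assess"), so readings end at discharge. Specific Aim #2 lists the same kind of daily readings and gives no summary either.

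**Opioids, by contrast.** The same section fixes a summary for the other primary outcome: "We will record the cumulative dose of opioids from 0 hours to 72 hours after the operation".

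**Power.** The Power Calculation section speaks of one primary outcome, opioid use. It sizes the trial on a 30% reduction against placebo, with 49 evaluable per arm. It gives no effect size for pain.

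**Tests.** Statistical Analysis compares pain scores, "opioid requirements, hospital length of stay, and PRQOL requirements will be compared using Mann-Whitney U tests". It mentions no time point, summary, baseline term or pair of arms. For continuous variables in general it says "Continuous variables will be reported using median and interquartile range due to their non-parametric nature", and the tests offered are Student's t-test "or a Wilcoxon signed rank test". The statistician is the person "who will determine the appropriate statistical tests for each outcome of interest".

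**Baselines and design.** VAS, PROMIS Pain Intensity 3a and HerQLes are all collected at baseline. Study Design describes three parallel arms, 1:1:1.

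**The concern.** A Mann-Whitney test takes one number per patient and two groups. For 72-hour pain the plan supplies four numbers and three groups, and no rule for reducing them. A favourable result on a declared primary outcome could then rest on one day, on all days or on an average, and on any pair of arms, chosen after the data are seen. This is the main part of the point.

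Two smaller matters sit in the same paragraph of the plan. Baseline values that the trial already pays to collect are not used in the comparisons of pain and quality of life, which gives up precision. And a paired test is named as the alternative to the t-test, although the arms are independent.

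**Working it through.** The plan has no figure of its own to reproduce here: 49 per arm concerns opioid use, and no pain effect, SD or correlation is given. The numbers below are illustrations.

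**Inputs.** From Power Calculation: 49 per arm and alpha 0.05, taken as two-sided. Assumed: between-day correlation ρ = 0.3, 0.5, 0.7; baseline-outcome correlation r = 0 to 0.5; d = 0.57, the standardised difference at which a two-sample t-test with 49 per arm has 80% power. Unless noted, each cell uses 10,000 simulated trials (Monte Carlo SE about 0.4 points for power, 0.2 for type I error).

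**1. Four days, one pair of arms, no true effect.** If the days were independent: 1 − 0.95⁴ = 18.5%. With correlation, Mann-Whitney on each day:

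| ρ | any day counts | all four days needed | one mean VAS |
|---|---|---|---|
| 0.3 | 17.1% | 0.0% | 4.8% |
| 0.5 | 15.7% | 0.1% | 4.9% |
| 0.7 | 13.7% | 0.5% | 5.0% |

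Data rounded and clipped to a 0-100 scale agree within 0.4 points. With d = 0.57 on every day, power is 46%, 51% and 58% if all four days are needed, and 98%, 93% and 88% for the mean. The reading rule alone can therefore decide the result.

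**2. What a mean loses if the effect is brief.** If k of the four days carry d, the standardised effect on the mean is k·d / (2√(1 + 3ρ)). At ρ = 0.5, k = 4 gives 4 × 0.57 / 3.16 = 0.72, and k = 1 gives 0.57 / 3.16 = 0.18. Simulated power of the mean with one active day is 12-16%, against about 78% for that day tested alone. With two active days it is 34-51%.

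**3. Three arms.** One mean VAS per patient, with all three pairs tested at 0.05, gives about 12% false positives. Four days by three pairs (12 tests) gives about 38%, 34% and 29% at ρ = 0.3, 0.5 and 0.7. A summary without a named contrast does not close the gap.

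**4. Averaging whatever readings exist.** Assume that pain falls 10 mm per day in every arm. The full mean is 15 mm below day 0. A patient without the day 3 reading averages 10 mm below (+5), and one without days 2 and 3 averages 5 mm below (+10). If half of the early leavers miss day 2 as well, the mean shift is (5 + 10)/2 = 7.5 mm. With 30% against 10% leaving early, the false difference is 0.20 × 7.5 = 1.5 mm; with 50% against 10%, 0.40 × 7.5 = 3.0 mm. In simulation (SD 25, ρ = 0.5, 4,000 trials) the rejection rate rises from 5% to about 7% and 10-11%. The Introduction's mean stay of 5.14 days in 30 patients suggests that few leave so early, but the share is not given.

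**5. Baseline term.** Rank ANCOVA regresses the ranks of the outcome on arm and the ranks of baseline. Power on normal data:

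| r | Mann-Whitney | rank ANCOVA | change (points) |
|---|---|---|---|
| 0 | 78.6% | 78.4% | −0.2 |
| 0.1 | 78.1% | 78.1% | 0.0 |
| 0.2 | 78.0% | 79.4% | +1.4 |
| 0.3 | 77.7% | 81.2% | +3.5 |
| 0.5 | 78.1% | 87.6% | +9.5 |

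A repeat with 4,000 trials per cell gave +3.9 at r = 0.3 and +8.9 at r = 0.5. Clipped and lognormal data give similar changes. Type I error is 4.4-5.6% for both methods. Linear ANCOVA is not a safe default: on lognormal data at r = 0.1 to 0.3 it falls 3-5 points (log SD 0.6) or 8-10 points (log SD 0.8) below Mann-Whitney.

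**6. Signed rank on independent arms.** With patients paired arbitrarily, average power is almost the same (77.1% against 77.8% for Mann-Whitney). But in about 26% of simulated data sets the verdict at 0.05 depended on which of 20 random pairings was used.

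**The case against.** **Opioid use is the real primary outcome.** Power Calculation speaks of a single primary outcome, so pain may be secondary and the stakes lower. This stands as far as it goes: the two sections conflict, and nothing says which governs. A reader might infer that pain is settled as an unpowered co-primary; the documents do not establish that.

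**The statistician will choose the tests.** The plan says so, but gives no date and no requirement that the choice precede unblinding. Choosing a test also does not define the quantity to be tested. This does not answer the point.

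**The 13-17% is hypothetical.** It is. A reader might infer that the plan runs an inflated error rate, but no section states an any-day rule. The figure shows how far the permissible readings differ.

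**Mann-Whitney without baseline is sound.** Correct. The arms are randomised, so a reader who infers bias or an invalid test goes too far. Only precision is lost, no correlation is documented, and the gain may be small for acute VAS.

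**A four-day mean suits only a lasting effect.** This stands. The Introduction itself describes plain bupivacaine as short-acting. It is a reason to choose the summary deliberately, not to leave it open.

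**Signed rank is a slip.** Probably so. It does not reach pain, opioids, length of stay or quality of life, which are assigned to Mann-Whitney.

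**Conclusion.** The point holds in three parts of unequal weight.

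- **Main part:** the 72-hour VAS comparison has no summary, no named pair of arms and no rule for early discharge, and the status of pain differs between two sections. For one pair of arms the false-positive rate could lie anywhere from near 0% (all days needed) to 13-17% (any day counts), against 5% for one fixed summary. This rests on assumed between-day correlations of 0.3 to 0.7.
- **Baselines:** the cost is precision only. Rank ANCOVA is worth about 0 points of power at r = 0 to 0.1, about 3 at 0.3 and about 9 at 0.5. These correlations are assumptions.
- **Signed rank:** a wording correction for the remaining continuous variables.

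Nothing here affects the opioid or length-of-stay analyses, or the sample size of 49, 54 and 162. The change should be made, and it is credible only if dated before unblinding.

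**What to change.** **(a) The 72-hour pain comparison.** Reconcile Outcomes of Interest with Power Calculation on whether pain is co-primary or secondary. Then add text to this effect:

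- Each patient has one 72-hour VAS summary, for example the mean of the day-of-surgery to day 3 readings, with the reading used on each day named (the day of surgery allows PACU or the nursing floor).
- The main contrast is Exparel against placebo, the contrast in Power Calculation. The other pairs are secondary or adjusted for multiplicity.
- Single-day VAS is descriptive.
- Readings missing after early discharge are handled by a method that accounts for day, and are reported by arm. Either impute by day and then form the summary, or use a repeated-measures model with day-by-arm terms. Choose one in advance. Do not simply average the available readings.

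**(b) Baselines.** Analyse the 72-hour VAS summary, 30-day PROMIS pain and HerQLes by rank ANCOVA, each on its own baseline. Keep medians and interquartile ranges as the description. If the repeated-measures model is chosen for VAS, put baseline VAS into it as a covariate instead.

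**(c) Wording.** Replace the Wilcoxon signed rank test by the Wilcoxon rank-sum (Mann-Whitney) test.

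**Cost.** Text in one section, a little more programming and no new data. There are three downsides. The gain from (b) is little or none if the baseline correlation is near zero. Rank ANCOVA yields a p-value but no difference in mm. A four-day mean dilutes an effect confined to one day, so an investigator who expects a brief effect should fix a different summary now.

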#### PLAN FOR OBTAINING INFORMED CONSENT

Screening for eligible subjects will be performed in clinic, by the participating surgeon (PI or Co-is), during preoperative evaluation. For each subject, written informed consent will be obtained before any protocol-related activities. As part of the informed consent procedure, the principal investigator, surgeon co-investigator, or one of the approved study coordinators will explain verbally and in writing the nature, duration, and purpose of the study in such a manner that the subject is aware of potential risks, inconveniences, or adverse effects that may occur. Subjects will be informed that they may withdraw from the study at any time and will receive all information required by federal regulations.

Following identification of a potential study participant, the investigator or the study coordinator will be responsible for instituting the informed consent process in a face-to-face manner. Before starting any study procedures, the investigator will discuss the proposed research study in detail with the potential subject during the office visit to discuss treatment options. The subject will be allowed ample time to read and review the informed consent document and ask questions. The informed consent document will be reviewed with the subject in depth by the participating investigator or designated member of the research team to ensure that the potential participant has a thorough understanding of the study protocol and understands the potential risks and benefits of study participation and his or her rights as a study participant. The investigators will be available by phone or office visit to answer any questions that the participant may have.

After consideration, the subject may return if necessary for another visit with the investigator and ask additional questions before signing the informed consent document to participate in this study.

After the subject has read and reviewed the informed consent document and has agreed to participate, he/she will be asked to sign and date the document. The study member obtaining consent will also sign and date the form, and documentation of the informed consent process will be included in the research file (i.e., the person who obtained consent, where and when consent was obtained, and who was present during the process). A copy of the consent form will be given to the subject for their records.

#### PROVISIONS FOR SUBJECTS FROM VULNERABLE POPULATIONS

The population to be studied includes adults of at least 18 years of age. Children, cognitively-impaired persons, pregnant women, and students and house staff under the direct supervision of the investigator are considered vulnerable populations and will, therefore, be excluded from participation. If a Cleveland Clinic Foundation staff member or employee is a potential candidate for the study, the subject will be informed during the consent process that his/her participation or refusal to participate will not influence grades, employment, or subsequent recommendations. We will only enroll individuals who can fluently communicate in the English language. If a subject cannot read a consent form due to illiteracy or blindness, a member of the research study staff will read and explain the consent form to the participant or the participant's legally authorized representative. A witness who will sign and date the consent form must be present during this encounter.

## SUBJECT PRIVACY AND DATA CONFIDENTIALITY

Subject anonymity and data confidentiality will be maintained throughout this study. Every effort will be made to maintain the confidentiality of documents that identify the subject by name (e.g., signed informed consent documents, clinic charts), except to the extent necessary to allow monitoring by the Office of Research Compliance at the Cleveland Clinic or by other regulatory authorities.

Much of the information collected, such as name or medical record number, will be stored in the AHSQC, a secure database that is used nationally to track clinical outcomes in patients who undergo hernia repair. Additional patient information will be recorded in RedCap®. Written consent forms and data collection forms will be stored in binders, which will stay in a locked office, at [name]. Randomization will occur with the use of a customized REDCap®, a secure network/firewall-protected electronic database for which only the investigator and the designated members of the study team will have access using an individually-assigned login and password. Only approved study members listed on the IRB protocol will have access to the separately-stored master list – which will be stored in a Cleveland Clinic password-protected computer and saved on an S drive. Only the Principal Investigator, Lead Research Coordinators, and Biostatisticians will be granted access to retrieve patient data for data quality assessment and data analysis. All electronic records pertaining to the clinical study will be password-protected and only approved study members listed on the IRB protocol will have password access.

### STUDY PROGRESSION / DATA SAFETY MONITORING

Progress of the study will be monitored internally by the research team. Weekly meeting between the PI, co-Is and research team will evaluate adverse events and study progression. Those will be reported to the IRB as appropriate.

### CLINICAL SIGNIFICANCE/INNOVATION

This trial will be among the first to investigate the outcome of TAP blocks with Exparel® or Bupivacaine hydrochloride versus placebo through a high-quality (double-blind, 3-arm, prospective, randomized controlled trial) in the field of abdominal wall reconstruction, with outcomes considered highly relevant for patients, surgeons, and hospital administrations.

Exparel® has various theoretical reasons for reducing hospital length of stay, including decreasing the use of oral and intravenous opioids. The average cost of 24 hours of inpatient care in Ohio is \$2,400-2,500 [18]. Decreasing patient's hospital stays would, therefore, afford medical systems a considerable cost advantage. However, previous studies suggesting that Exparel® may be associated with decreased hospital costs have frequently been unblinded, uncontrolled, and retrospective in nature with Exparel® packaged as part of a multimodal postoperative recovery program [19]. Such actions do not isolate the effects of each intervention and difficult to draw significant conclusions about the role of Exparel® in a multimodal pain management strategy. The outcome of this study will help to determine the role of Exparel® in postoperative analgesia of procedures with major abdominal incisions.

